### **9.3.2 Analysis of the secondary efficacy endpoints**

The secondary efficacy variables supporting the primary efficacy variable are listed below, and will be included in the multiplicity adjustment:

1. Proportion of study participants who achieve HiSCR75 at Week 16. A similar analysis to the primary responder analysis will be performed.
  - a. bimekizumab 320mg Q2W vs placebo
  - b. bimekizumab 320mg Q4W vs placebo
2. Absolute change from Baseline in DLQI Total Score at Week 16. Analysis will be based on an analysis of covariance (ANCOVA) with treatment and stratification variables as fixed effects and the Baseline values as covariate.
  - a. bimekizumab 320mg Q2W vs placebo

---

- b. bimekizumab 320mg Q4W vs placebo
- 3. Absolute change from Baseline in Skin Pain Score at Week 16, as assessed by the “worst pain” item (11-point numeric rating scale) in the HSSDD. Analysis will be based on an ANCOVA with treatment and stratification variables as fixed effects and the Baseline values as covariate.
  - a. bimekizumab 320mg Q2W vs placebo
  - b. bimekizumab 320mg Q4W vs placebo
- 4. Pain response (defined as a decrease from Baseline in HSSDD weekly worst skin pain score at or beyond the threshold for clinically meaningful change) at Week 16. A similar analysis to the primary responder analysis will be performed.
  - a. bimekizumab 320mg Q2W vs placebo
  - b. bimekizumab 320mg Q4W vs placebo

[figure not shown]
To control the overall type I error rate at 0.05 for the multiple comparisons in the primary and secondary efficacy variables, a closed testing procedure under a parallel gatekeeping framework will be applied ([Sun, 2018](#)).

Under this framework, each bimekizumab dose of 320mg Q2W and 320mg Q4W will be compared to placebo in the first instance at a familywise error rate of 0.025 ( $\alpha/2$ ). Simultaneously within each dose, closed testing for the primary and secondary efficacy endpoints will be performed as follows:

- 1. Step 1: Test  $\text{HiSCR}_{50}$  at significance level 0.025.
- 2. Steps 2 to 5 – If Step 1 is significant at 0.025 then test each secondary endpoint sequentially in the order shown below, moving to the next step only if significance achieved at 0.025.
- 3. In the event that Step 5 is significant at 0.025 for a given dose, then Steps 1 to 5 will be repeated for the other dose using a significance level of 0.05.

A schematic of the procedure is shown in [Figure 9–1](#).

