## **9.3 Planned efficacy/outcome analyses**

### **9.3.1 Analysis of the primary efficacy endpoint**

The primary objective of this randomized, double-blind, placebo-controlled, multicenter, pivotal study in study participants with moderate to severe HS is to compare the efficacy of bimekizumab 320mg Q2W and bimekizumab 320mg Q4W with placebo at Week 16. For the purposes of Week 16 analyses, the bimekizumab treatment arms of 320mg Q2W/Q2W and bimekizumab 320mg Q2W/Q4W treatment groups will be pooled.

The primary and secondary efficacy analyses will be performed based on the RS.

The primary endpoint is the HiSCR50 response at Week 16. The primary efficacy analysis will evaluate the composite estimand in the RS. The composite estimand combines the clinically meaningful improvement from Baseline based on the HiSCR50 response and early receipt of

systemic antibiotic rescue medication, or discontinuation of IMP due to an AE or lack of efficacy.

The following 4 attributes describe the estimand that will be used to define the treatment effect of interest for the primary efficacy analysis:

4. Population=Study participants meeting the protocol-specified inclusion/exclusion criteria.
5. Study participant-level outcome=HiSCR50 at Week 16.
6. Intercurrent event handling=An intercurrent event is defined as receipt of systemic antibiotic rescue medication or discontinuation of study treatment due to an AE or lack of efficacy prior to Week 16. A composite strategy will be implemented in which a positive clinical outcome is defined as achieving HiSCR50 at Week 16 and not receiving systemic antibiotic rescue medication, and not discontinuing study treatment due to an AE or lack of efficacy through Week 16. Any missing data at Week 16 that are not preceded by an intercurrent event will be imputed using multiple imputation.
7. Population-level summary measure=conditional odds ratio comparing bimekizumab to placebo adjusted for stratification factors used in the randomization.

As a sensitivity analysis, any missing data at Week 16 that are not preceded by an intercurrent event (ie, receipt of systemic antibiotic rescue medication, or discontinuation of IMP due to an AE or lack of efficacy) will be imputed as non-response.

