## **9.8       Determination of sample size**

A total of 490 study participants will be randomly assigned in a 2:2:2:1 ratio to the following treatment arms:

- Bimekizumab 320mg Q2W during Initial Treatment Period (Weeks 0-16) and Maintenance Treatment (Weeks 16-48) Periods, N=140
- Bimekizumab 320mg Q2W during Initial Treatment Period (Weeks 0-16), and Bimekizumab 320mg Q4W during Maintenance Treatment Period (Weeks 16-48), N=140
- Bimekizumab 320mg Q4W during Initial Treatment (Weeks 0-16) and Maintenance Treatment Periods (Weeks 16-48), N=140
- Placebo during Initial Treatment Period (Weeks 0-16), and Bimekizumab 320mg Q2W during Maintenance Treatment Period (Weeks 16-48), N=70

The analysis of the primary efficacy endpoint and secondary efficacy endpoints are based on a comparison of bimekizumab versus placebo at Week 16, with alpha adjustment strategy as indicated in Section 9.3.1 and Section 9.3.2.

The power to detect a statistically significant difference for each of the endpoints are shown in Table 9-1. Notably, with a 2-sided significance level of 0.025, the sample size of 140:70

provides 73% power for detecting at least a difference of 1.5 (bimekizumab Q4W vs placebo) for the Worst Pain change from Baseline (CFB) endpoint.

Given the high level of power for each of the primary and key secondary endpoints at the 0.025 significance level for the Q2W comparison (power $\geq$ 0.89), and per the alpha spending strategy, there is a high likelihood that the Q4W comparison of Worst Pain CFB vs placebo will be allowed to be tested against the 0.05 level of significance. The power for this latter test is 81%. The sample size is thus ultimately driven by the Worst CFB endpoint. Furthermore, the randomization ratio of 2:2:2:1 has been chosen to provide study participants with a high probability (6/7 ~ 86%) of being randomized to active study drug.

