**Table 9–1: Power calculation assumptions and methods**

Endpoint	Power $\alpha = 0.025$ , 2-sided		Assumptions		
	Q2W	Q4W	Week 16 Bimekizumab Q2W N=280 a	Week 16 Bimekizumab Q4W N=140	Week 16 Placebo N=70
HiSCR 50	0.99	0.90	Proportion responders=0.60	Proportion responders=0.50	Proportion responders=0.25
HiSCR 75	0.99	0.98	Proportion responders=0.45	Proportion responders=0.35	Proportion responders=0.10
DLQI	0.99	0.96	Mean CFB=-5.4; SD=6.8	Mean CFB=-4.8; SD=6.8	Mean CFB=-0.8; SD=6.6
Worst Pain CFB b	0.89	0.73	Mean CFB=-2.2; SD=3.2	Mean CFB=-2.0; SD=3.2	Mean CFB=-0.5; SD=3.7
Worst Pain Response c	0.95	0.53	Proportion responders=0.53	Proportion responders=0.43	Proportion responders=0.23

CFB=change from Baseline; Q2W=every 2 weeks; Q4W=every 4 weeks; SD=standard deviation

Note: Estimates for HS0003 are based on Week 12 data from the HS0001 study.

a Pooled Q2W at Week 16 from Q2W/Q2W and Q2W/Q4W arms

b Within-subject average of Worst Pain according to 24-hour recall

c Assumes N=208, 104, 52 in Q2W, Q4W, and placebo, respectively, to account for Worst Pain score at or above the threshold for clinically meaningful change from Baseline

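### The worst-pain ANCOVA would be safer with an arm-specific or robust variance: at the planning SDs, one pooled residual variance makes the standard error up to about 9% too small

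*Protocol*

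**What the plan says.** Worst-pain change from Baseline at Week 16 is a ranked secondary endpoint, fourth in the testing sequence for each dose. Protocol Section 9.3.2 gives its model as follows: "Analysis will be based on an ANCOVA with treatment and stratification variables as fixed effects and the Baseline values as covariate". The same model is named for DLQI. Nothing is said about the residual variance structure or the type of standard error.

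The group sizes come from three places. Section 9.8 states "A total of 490 study participants will be randomly assigned in a 2:2:2:1 ratio". Section 9.3.1 adds that for Week 16 "the bimekizumab treatment arms of 320mg Q2W/Q2W and bimekizumab 320mg Q2W/Q4W treatment groups will be pooled". Table 9-1 therefore heads its columns "Week 16 Bimekizumab Q2W N=280", "Week 16 Bimekizumab Q4W N=140" and "Week 16 Placebo N=70", a 4:2:1 split.

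For this endpoint Table 9-1 assumes mean changes of -2.2 (Q2W) and -2.0 (Q4W), each with SD 3.2. For placebo it assumes "Mean CFB=-0.5; SD=3.7". The table notes that these values come from Week 12 of the Phase 2a study HS0001. The stated powers at two-sided 0.025 are 0.89 (Q2W) and 0.73 (Q4W). Section 9.8 adds 81% for Q4W at 0.05.

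The gatekeeping procedure in Section 9.3.2 is introduced "To control the overall type I error rate at 0.05 for the multiple comparisons in the primary and secondary efficacy variables".

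**The concern.** When one residual variance is estimated across all arms, the large arms dominate it. Here the large arms are the less variable ones on the plan's own assumptions, and the resulting variance is then applied to a placebo arm that is both smallest and most variable. Placebo enters both comparisons and contributes most of the standard error, so the model reports too small a standard error for each.

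The power figures appear to allow for unequal SDs, while the analysis section names a model that by default does not. What is at stake is the width of the confidence intervals and the level of the worst-pain test. Section 9.8 says this endpoint drives the sample size, and it gates both pain response and the passing of alpha to the other dose.

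**Working it through.** **Inputs.** n = 280, 140, 70; SD = 3.2, 3.2, 3.7; differences from placebo 2.2 - 0.5 = 1.7 (Q2W) and 2.0 - 0.5 = 1.5 (Q4W), all from Table 9-1. Alpha is 0.025 two-sided per dose, or 0.05 for the second dose if alpha is passed on (Section 9.3.2).

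**1. Reproducing the stated power.** With unequal variances, SE = sqrt(s1²/n1 + s0²/n0), Satterthwaite degrees of freedom and a noncentral t:
- Q2W: SE = sqrt(3.2²/280 + 3.7²/70) = 0.482, df 96.4.
- Q4W: SE = sqrt(3.2²/140 + 3.7²/70) = 0.518, df 121.8.

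The equal-variance alternative pools the SD over the two arms by degrees of freedom (3.305 for Q2W, 3.374 for Q4W).

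| Comparison | Stated | Unequal variance | Equal variance |
|---|---|---|---|
| Q2W at 0.025 | 0.89 | 0.893 | 0.944 |
| Q4W at 0.025 | 0.73 | 0.733 | 0.781 |
| Q4W at 0.05 | 0.81 | 0.819 | 0.856 |

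The first two figures match the unequal-variance test. The third is close to it (0.819 rounds to 0.82) and well short of the equal-variance value.

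**2. Standard error under one pooled variance, equal means.** For a single three-arm model the pooled variance is (279 × 3.2² + 139 × 3.2² + 69 × 3.7²)/487 = 10.73, SD 3.28. Model SE = sqrt(pooled variance × (1/n1 + 1/70)). Actual error = 2 × (1 - Φ(z × model SE / true SE)), with z = 2.2414 at 0.025 and 1.960 at 0.05.

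| Model | Comparison | Model SE | True SE | Ratio | Error at 0.025 | Error at 0.05 |
|---|---|---|---|---|---|---|
| Three-arm | Q2W | 0.438 | 0.482 | 0.908 | 0.042 | 0.075 |
| Three-arm | Q4W | 0.479 | 0.518 | 0.925 | 0.038 | 0.070 |
| Pairwise | Q2W | 0.442 | 0.482 | 0.917 | 0.040 | 0.072 |
| Pairwise | Q4W | 0.494 | 0.518 | 0.953 | 0.033 | 0.062 |

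**3. Dependence on the placebo SD** (three-arm model, active SD 3.2, nominal 0.025):

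| Placebo SD | Q2W | Q4W |
|---|---|---|
| 2.88 (ratio 0.9) | 0.016 | 0.018 |
| 3.2 | 0.025 | 0.025 |
| 3.4 | 0.031 | 0.030 |
| 3.7 | 0.042 | 0.038 |
| 3.9 | 0.049 | 0.044 |

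**4. Simulation.** Three-arm ANCOVAs with Baseline and two binary strata, 20,000 data sets per scenario, gave 0.041-0.047 (Q2W) and 0.039-0.042 (Q4W) at nominal 0.025. The upper ends arise when Baseline explains the same absolute variance in every arm, which widens the gap between residual SDs. HC3 standard errors in the same model gave 0.024-0.026 at 0.025 and 0.049-0.050 at 0.05.

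**5. DLQI.** With SD 6.8 on active and 6.6 on placebo, the three-arm calculation gives 0.022 and 0.023, slightly conservative.

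All error rates assume complete data; the multiple imputation of Section 9.6 was not modelled.

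**The case against.** The strongest reply is that the text contains no error. It says ANCOVA and leaves the variance structure open. Section 9 defers detail to the SAP, and treatment-specific variances or HC3 would be consistent with Section 9.3.2 as written. This stands: the pooled variance is the default meaning of ANCOVA, not something the protocol states.

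The SDs are also uncertain. They are Phase 2a planning values. The adverse-event percentages in Section 2.3 fit about 21 placebo and 46 bimekizumab participants. If the pain SDs came from similar numbers (an assumption), the SD ratio of 3.7/3.2 = 1.16 has a 95% interval of about 0.81 to 1.74, which settles neither inequality nor its direction. Sections 2.3 and 4.3 describe HS0001 as using 320mg Q2W, so the Q4W SD looks carried over. This stands too.

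Third, the SDs accompany assumed treatment effects. If bimekizumab left pain wholly unchanged, the arms would share one distribution and the test would hold its level. Inflation needs equal means with unequal SDs, and the test is reached only after the three earlier steps succeed. That narrows the type I error argument. It does not remove the effect on intervals, which are too narrow whenever placebo is the more variable arm, whatever the mean difference.

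Finally, entering arm-specific SDs in a two-sample power formula is a planning approximation that ignores Baseline and strata, and does not define the analysis. A reader might infer a contradiction between Sections 9.8 and 9.3.2. The documents support only a difference in variance assumption, and only if the default ANCOVA is used.

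**Conclusion.** The point holds as a conditional weakness in the model for one secondary endpoint. If a single residual variance is used and the planning SDs hold, the standard error is about 8-9% too small in a three-arm model, or 5-8% in pairwise models. The error for equal mean pain change is then about 0.040-0.042 (Q2W) and 0.033-0.038 (Q4W) against 0.025. At a placebo SD of 3.4 it is about 0.03, at equal SDs there is no inflation, and at a smaller placebo SD the test is conservative.

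A reader might infer that the test will run at about 0.04, or that the overall 0.05 level is broken. Neither follows. The chance of a false worst-pain claim for either dose reaches 0.058-0.064 only if both doses lack a mean pain effect, both pass all earlier steps, and the SDs differ as planned. The primary endpoint, HiSCR75 and pain response use logistic regression and are not affected; DLQI is essentially unaffected. This is an optional improvement, not a must-fix.

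**What to change.** For the ranked continuous endpoints, keep the ANCOVA mean model and add one sentence on variance. Specify either treatment-specific residual variances with Satterthwaite or Kenward-Roger degrees of freedom, or HC3 standard errors, applied in each imputed data set before combining by Rubin's rules. It should be fixed before unblinding; if the SAP already says this, nothing further is needed.

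The cost is a sentence and a software option. If the SDs are in fact equal at 3.2, Q2W power at 0.025 falls from 0.957 (pooled) to 0.954 (unequal-variance), about 0.3 percentage points. Nothing is lost against the stated 0.89 and 0.73, which already correspond to an unequal-variance test, and the test and interval then remain valid whichever way the SDs differ.

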**Figure 9–1: Closed Testing Procedure**

AN=abscess and inflammatory nodule; CFB=change from Baseline; DLQI=Dermatology Life Quality Index;  $\text{HiSCR}_{50}$ =a 50% reduction in the total AN count with no increase from Baseline in abscess or draining tunnel count;  $\text{HiSCR}_{75}$ =a 75% reduction in the total AN count with no increase from Baseline in abscess or draining tunnel count; HS=hidradenitis Suppurativa; Q2W=every 2 weeks; Q4W=every 4 weeks

### 9.3.3 Other efficacy/other outcome analyses

Analyses of the other efficacy measures will be detailed in the SAP.

### 9.3.4 COVID-19 impact analysis

To assess the impact of the COVID-19 pandemic on the primary efficacy endpoint analysis, the following additional sensitivity analyses will be performed:

- Imputation as nonresponse for any missing data due to COVID-19 at Week 16 and analyzed using the same analysis model as for the primary analysis
- Separate inferential analysis of the primary and secondary efficacy endpoints based on the COVID-19 Free Set
- Separate summary statistics for the primary efficacy endpoint at Week 16, based on the COVID-19 Free Set
- Summary of the number of study participants with missing primary or secondary endpoint data, as applicable

In addition, to assess the broader impact of the COVID-19 pandemic on the study, the following summaries will be presented:

- Summary of study participant disposition based on enrollment before, during, and after COVID-19 pandemic onset
- A summary of study visits impacted by the COVID-19 pandemic
- A summary of protocol deviations related to COVID-19

Any additional COVID-19 related analyses will be specified in the study SAP. Note: the date of COVID-19 pandemic onset is defined as 11 March 2020, the date that the World Health Organization declared the COVID-19 pandemic. The end date of the COVID-19 pandemic end will be defined in the study SAP, if applicable.

## **9.4 Planned safety and other analyses**

### **9.4.1 Safety analyses**

All TEAEs, SAEs, TEAEs leading to discontinuation, AEs of special interest (eg, cases meeting Hy's Law criteria), and other safety topics of interest (Section 8.3.7) will be collected during the study and for up to 20 weeks after the last dose of IMP (for study participants who do not participate in the extension study, HS0005). Safety analyses will be carried out using the Safety Set (study participants who received at least 1 full or partial dose of IMP). Summaries of Confirmed and Suspected COVID-19 TEAEs, respectively, will be presented. The definition of Confirmed and Suspected COVID-19 TEAEs will be provided in the SAP.

### **9.4.2 PK and ADAb analyses**

Plasma concentrations of bimekizumab will be summarized by treatment group at each timepoint using descriptive statistics. In addition, PK model-based analyses may be performed.

Antidrug antibody data will be evaluated for each study participant and each regimen, and rates and classification of ADAb-positive study participants will be calculated.

## **9.5 Handling of protocol deviations**

Important protocol deviations are identified as part of the data cleaning process as specified in the study-specific data cleaning schedule/plan. Ongoing, blinded data cleaning meetings will be held throughout the duration of the study. Objectives of these meetings include to review protocol deviations and to document potential impact that these deviations might have on the study objectives. Furthermore, overall trends in protocol deviations will be discussed at the Data Evaluation Meeting(s). Through this ongoing data cleaning and evaluation process, all decisions regarding important protocol deviations are made on an ongoing basis. Protocol deviations (eg, missing assessments or visits) related to COVID-19 will be listed and summarized separately.

## **9.6 Handling of dropouts or missing data**

The analyses for the primary and secondary efficacy variables will include the use of multiple imputation. In multiple imputation, the missing value is replaced by a set of plausible values, where each value is a Bayesian draw from the conditional distribution of the missing data given the observed data.

Intermittent missing data will be imputed using the Markov-Chain Monte Carlo method, followed by regression for monotone missing data. The multiple imputation procedures planned for the primary and secondary efficacy analyses are based on an assumption of data missing at random.

The sensitivity of results to the approach for handling missing data will be evaluated via supportive analyses using different missing data mechanisms. The following supportive analyses for the primary efficacy variable will be conducted:

1. Deviations from the missing at random pattern will be evaluated using a reference-based multiple imputation approach. Intermittent missing data will be imputed using the Markov-Chain Monte Carlo method. The remaining monotone missing data will be assumed to follow a missing not at random pattern. These data will be imputed using a reference-based approach in which the multiple imputation model is based on data from the placebo group, thereby assuming that monotone missing data follow a trajectory similar to the placebo group.
2. Tipping point analyses will be performed to evaluate missingness assumptions. Various delta adjustments will be made to the assumed responses on the monotone missing data in each treatment group independently with various degrees of plausibility. It will include scenarios where study participants who have missing data and are randomized to bimekizumab have a lower probability of response compared to study participants who have missing data and were randomized to placebo. For binary variables, this includes the worst case scenario where study participants who have missing data and are randomized to bimekizumab are considered nonresponders, while study participants who have missing data and were randomized to placebo are considered responders. The goal of the tipping point analysis is to systematically vary assumptions until there is no evidence of a treatment effect (if possible). The plausibility of such required delta adjustment will then be assessed.
3. The treatment policy strategy for addressing intercurrent events will be considered. This will be based on an analysis of all available data at Week 16 regardless of the occurrence of intercurrent events. This analysis will use the same models specified for the primary analysis, where study participants are analyzed according to their randomized treatment, even if they discontinued study treatment for any reason prior to Week 16. Even though efforts will be made to collect the primary outcome data for all study participants at Week 16, there may still be some study participants for whom Week 16 efficacy data cannot be obtained. In this case, missing data will be imputed using multiple imputation under the assumption of MAR. Results will be combined into a single inference using Rubin's rule. It should be noted that this measures something different from the primary analysis and could be confounded by placebo study participants who withdraw and are subsequently on another active medication at the time of the Week 16 assessment. Therefore, the results of this analysis should be interpreted in the appropriate context.
4. An additional supportive analysis will be based on observed data only for study participants who are still on the randomized treatment at Week 16. Study participants with missing data or who have prematurely discontinued study treatment will be treated as missing. The same procedure described as in the primary efficacy analyses will be used.

All imputation of other missing data will be detailed in the SAP.

## **9.7       Planned interim analysis and data monitoring**

### **9.7.1       Data Monitoring Committee**

An independent DMC will periodically review unblinded efficacy and safety data to assess the benefit/risk of bimekizumab in study participants with moderate to severe HS. Individual study participant-level efficacy data listings may be provided to the DMC to put the safety review in the context of risk/benefit. Any data to be provided will be specified per the DMC charter. ■

